4.3 Exclusion Criteria

Clinics will be excluded from participation in the study based on the following criteria:

- Provide only specialty care (e.g. addiction medicine, behavioral health)
- Have fewer than 35 patients receiving MAT for OUD
- Do not have an established EHR or cannot provide appropriate access to allow integration of OARS within the clinic's EHR

5 STUDY PROCEDURES

The OARS platform is owned and maintained by Q2i. For the purpose of conducting this study, Q2i is partnering with researchers from the UCLA Departments of Family Medicine and Psychiatry and Biobehavioral Sciences to execute the research at each of the six participating clinics.

The research team, composed of study staff at both Q2i and UCLA, will determine the order of implementation of the OARS platform by clinic. Study staff will then notify each clinic of the start date of the OARS platform implementation for their clinic. Following start date assignment, the baseline phase of the study will commence in which patients will receive standard treatment for OUD provided by each clinic (TAU).

Data collected will include both patient-level indicators from each clinic's EHR (see data collection tool) and provider-level indicators obtained from interviews with PCPs. Baseline data will provide an assessment of TAU for up to a period of four (clinics one and two), eight (clinics three and four), and 12 (clinics five and six) months prior to implementation of the OARS platform. Study staff will provide each clinic with relevant data collection specifications and each clinic's IT staff will be responsible for submitting requested data elements from the clinic's EHR to Q2i through secure file transfer. Up to two PCPs from each clinic will be interviewed (see semi-structured interview guides) during TAU, at one month after OARS implementation, and at the end of the OARS period. Eligible PCPs will receive a recruitment letter that outlines the study activities with a request for interested providers to contact study staff at UCLA.

Concurrently with baseline data collection, study staff will also work with clinics to initiate the OARS platform according to the determined start date. Clinics will begin using the OARS platform with all MAT patients seen at that time. Therefore, patients receiving TAU when the OARS platform is implemented will shift care to using OARS. Patient care and treatment of OUD will then commence under the OARS condition for a period of eight months for each clinic. To compare outcomes under the OARS condition to those that occurred under TAU, comparable data will be directly collected through the OARS platform. Additionally, patient-level data collected during the OARS condition will be used to assess to what extent different levels of provider and patient engagement with OARS relate to opioid abstinence among patients. Data elements of interest (patient demographics, medications, and billing information) that are not transmitted through OARS will be obtained from each clinic's EHR and delivered directly to Q2i through secure file transfer.

All patient-level data will be collected via the EHR and transmitted to Q2i study staff via a secure file transfer system. Patients' medical record identifier will be included in each of the data transmissions to link data across TAU and OARS conditions. No one outside of the Q2i engineer will have access to patient identifiers across both conditions. Patients will not be required to submit any data for the purpose of this research. Providers will be interviewed by UCLA study staff. Interviews will be transcribed and the transcripts will be de-identified prior to sharing with Q2i staff.

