3 STUDY DESIGN

3.1 Description of Study Design

This study tests whether MAT in the primary care setting delivered via the OARS platform can result in improved clinic-level outcomes compared to TAU using a stepped-wedge effectiveness trial design (see Figure 1). This design facilitates data collection on patient outcomes prior to implementation of OARS, data that is individual to each clinic and that will serve as baseline values. In turn, baseline data collected under TAU will be compared to corresponding data collected through OARS for the purpose of assessing whether OARS use results in improved outcomes. This study design necessitates data collection only through EHR data review and abstraction; no information is required directly from patients for the purpose of this study.

Figure 1. Study Design

	Months 1-4	Months 5-8	Months 9-12	Months 13-16	Months 17-20
Clinic					
1	TAU		OARS		
2					
3	TAU		OARS		
4					
5	TAU			OARS	
6					

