3.2 Summary of Study Endpoints

The following primary outcomes will be assessed under TAU and OARS conditions:

- 1) Number of patients PCPs can treat using MAT in primary care settings;
- 2) Retention in treatment (number of patient visits kept with PCPs, length of stay in treatment);
- 3) Proportion of opioid-free urine tests.

The secondary outcome of opioid abstinence, defined as opioid-negative urine toxicology, will be assessed on a patient level as patients are treated for OUD under the OARS condition.

Exploratory outcomes will include additional elements from several administrative sources, namely meta-data from OARS software and additional detail on records of service delivery from the providers'

electronic health records, claims database, and OARS. OARS meta-data will primarily be time stamps around key service delivery or key OARS activities to account for differences in time spent during traditional clinical service delivery and possible additional wrap-around activities. Service delivery measures will include the number of units of different services provided to each patient over time.

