4.2 Inclusion Criteria

The research conducted in this study involves a review of patient medical records. In each clinic, the research team will work with clinic administrators to identify PCPs and patients treated by the PCPs using MAT who will contribute data to baseline and who will use the OARS platform when it is integrated into the EHRs at the determined date.

Clinics will need to meet the following criteria to participate in the study:

- Provide treatment to patients in the setting of primary care (e.g. family medicine, internal medicine)
- Have at least one provider with a DATA-2000 waiver who provides primary care and MAT to patients
- Have at least 35 patients receiving MAT for OUD
- Have an established EHR

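### No rule is given for the order in which clinics go live; an order related to clinic trends could shift the estimate under some models, and a random draw with period terms would guard against it

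*Combined protocol and SAP*

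**What the plan says.** Section 3.1 describes a study "using a stepped-wedge effectiveness trial design" and does not call it randomised. Section 5 gives the allocation step: "The research team, composed of study staff at both Q2i and UCLA, will determine the order of implementation of the OARS platform by clinic". The same section says "The OARS platform is owned and maintained by Q2i". On timing it says "Following start date assignment, the baseline phase of the study will commence", so go-live dates are known before any baseline data are collected for the study.

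Usual care lasts 4, 8 or 12 months for successive pairs of clinics. Treatment then continues "under the OARS condition for a period of eight months for each clinic". Pairs therefore go live at months 5, 9 and 13.

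None of Sections 1 to 7 mentions a random draw, an independent allocator, stratification or a readiness rule for the order. The front matter was not available to check.

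Section 6.3 compares an index visit, which it does not define, with six months after implementation. It also plans repeated-measures analyses with OARS against usual care as the main predictor. It will consider clinic size, age of the MAT program and ancillary services, and it names no calendar-time term.

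**The concern.** In a stepped wedge, the order decides which clinics supply early OARS data and which supply late usual-care data. A random order makes that unrelated, on average, to how clinics were already changing. Here the protocol names who decides but not how, and some of the deciders work for the platform's owner.

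The team will know something about each clinic before it sets dates. Eligibility requires a clinic to "Have at least 35 patients receiving MAT for OUD", which bears on the first primary outcome ("Number of patients PCPs can treat using MAT in primary care settings"). Clinics are excluded if they "cannot provide appropriate access to allow integration of OARS". Neither fact is a trend, but either could be used to schedule clinics, and nothing in the text prevents it.

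Stable differences in level between clinics cancel in a within-clinic comparison. Differences in trend may not, and a main effect for a fixed clinic factor such as size does not remove them. What is at stake is whether part of an estimated OARS effect could come from the rollout order.

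**Working it through.** **Inputs.** Section 5 gives 4, 8 or 12 months of usual care, then 8 months of OARS, with two clinics per date. Time in study is 4 + 8 = 12, 8 + 8 = 16 and 12 + 8 = 20 months, which agrees with the 12 to 20 months in Section 3.4. Clinic-months total 2 × (12 + 16 + 20) = 96, of which 6 × 8 = 48 are under OARS. Possible orders: 6!/(2!2!2!) = 90.

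**Assumption.** The documents give no clinic trends. Let the true OARS effect be zero. Two clinics improve by d units per month, two by d/2 and two not at all, so the mean slope is d/2. Results below use d = 1 and scale in proportion to d. The orders compared are the two extremes: fastest-improving clinics first, and fastest last.

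**Clinic and calendar-period effects (least squares).** The OARS estimate picks up each clinic's slope per four-month period with coefficient 0.2353 (first date), 0.0588 (middle) or -0.2941 (last). Monthly slopes are multiplied by 4. Month terms give the same figures.
- Fastest first: 4 × (2 × 0.2353 × 1 + 2 × 0.0588 × 0.5) = +2.12.
- Fastest last: 4 × (2 × (-0.2941) × 1 + 2 × 0.0588 × 0.5) = -2.12.
- The coefficients sum to zero, so the mean over the 90 orders is 0. By enumeration the SD is 0.96, and 36 of the 90 orders have a bias of at least 1 in absolute size.
- For d = 0.25 and 0.5 the extremes are ±0.53 and ±1.06.

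**Clinic effects only.** With T months of usual care and 8 of OARS, the midpoints of the two phases are (T + 8)/2 apart: 6, 8 and 10 months. Each clinic is weighted in proportion to 8T/(T + 8): 2.667, 4 and 4.8, or 0.233, 0.349 and 0.419 by pair.
- Fastest first: 0.233 × 6 × 1 + 0.349 × 8 × 0.5 = +2.79.
- Fastest last: 0.419 × 10 × 1 + 0.349 × 8 × 0.5 = +5.58.
- Mean over the 90 orders: 0.5 × (0.233 × 6 + 0.349 × 8 + 0.419 × 10) = +4.19, SD 0.62.

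**Before-after contrast, sixth OARS month minus index, averaged over six clinics.**
- Index at the go-live month: 5 months × 0.5 = +2.5 in every order.
- Index at the last usual-care month: 6 × 0.5 = +3.0 in every order.
- Index at study month 1: elapsed time is 9, 13 or 17 months. Fastest first gives (2 × 9 × 1 + 2 × 13 × 0.5)/6 = +5.17; fastest last gives (2 × 17 × 1 + 2 × 13 × 0.5)/6 = +7.83.

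**Level differences only** (10, 5 and 0 units by pair, no trends): bias is 0 in both regression models, whatever the order.

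**The case against.** The strongest reply is that nothing shows a biased order. Academic staff share the decision, and dates precede baseline, so the order cannot react to study data. The 35-patient threshold and EHR access are not trends. All of this stands. What remains is a missing safeguard: prior knowledge of the clinics could still inform the schedule, and the protocol would allow it.

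A second reply is that order may not matter for the planned analysis. If the index visit is tied to go-live, the before-after contrast has the same bias in all 90 orders. That also stands. But the index visit is undefined, and the planned repeated-measures analysis could take a form in which order does matter.

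A third reply is that the missing calendar-time term is the larger problem. In the example this is correct: with clinic effects only, the average bias under random order (+4.19) exceeds the swing due to order (5.58 - 2.79 = 2.79). The two changes therefore belong together.

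A reader might infer from the ownership that the order would be chosen to favour the product. The documents do not support that, and the figures give no consistent direction. Fastest-first gives the favourable bias when period terms are fitted, but the smaller of the two biases when they are not.

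**Conclusion.** The gap is real: the protocol does not say how the order is set, and any order the team chooses would comply. Confidence in that reading of the text is high. That the order is related to clinic trends, or that the estimate is biased, is not shown.

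If such a relation existed, its size and direction would depend on a model that Section 6.3 leaves open. The extremes for d = 1 are +2.12 and -2.12 with clinic and month terms, +2.79 and +5.58 with clinic effects only, and no difference between orders for a contrast anchored at go-live. These figures rest on assumed linear trends, a zero true effect and the two extreme orders of 90. The unit is generic because the primary outcomes are on different scales.

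Two stronger readings should be resisted. One is that an order tied to trends must shift the estimate; the go-live contrast shows otherwise. The other is that randomising alone would cure the problem; it centres the bias on zero only when period terms are fitted. This is a cheap improvement worth making before the dates are set, since the order cannot be changed afterwards.

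**What to change.** **Section 5.** State that the six enrolled clinics are allocated at random, two to each go-live date, by a computer-generated sequence held by someone independent of Q2i and fixed before baseline starts. Analyse clinics by assigned sequence and record any departure from it.

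**Section 6.3.** Include clinic and calendar-period terms in the primary model. The draw removes systematic selection; the period terms remove the common time trend.

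**If EHR-integration readiness must govern the order.** Fix the rule in writing before baseline, report the study as a non-randomised rollout, and still fit the period terms.

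**Cost.** One draw and a few sentences. Some freedom to schedule clinics by readiness is lost; the documents give no integration times, so how much is unknown. Chance imbalance among six clinics remains (SD 0.96 in the example with period terms).

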7.3 Informed Consent Process

The research team is requesting a waiver of consent for patient participants since this research involves no more than minimal risk and involves no procedures for which written consent is normally required outside of the research context. The risk of contacting patient participants and documenting their informed consent provides a possible risk of breach of confidentiality since there is no other need to contact patient participants. Therefore, this risk is determined to be greater than the risk of the study procedures. Additionally, informed consent would not be possible within this study design since the primary outcomes are meant to be evaluated with each clinic's entire patient population. Requiring informed consent may actually result in biased results since individuals who choose to consent (or not consent) may have a different probability of experiencing the outcomes of interest.

In addition, UCLA study staff will obtain verbal consent from provider participants who choose to participate in the semi-structured interview. The verbal consent process, and the interview that follows, will be conducted over a secure Zoom line to ensure participant confidentiality.

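### The plan does not settle whether patients active at go-live who never return count under OARS; if they drop out, per-patient retention for carried-over patients is biased upward

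*Combined protocol and SAP*

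**What the plan says.** Section 5 gives the entry rule at go-live: "Clinics will begin using the OARS platform with all MAT patients seen at that time". The next sentence reads: "Therefore, patients receiving TAU when the OARS platform is implemented will shift care to using OARS". The plan does not say whether being seen means attending a visit or being under the clinic's care.

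On the data source, Section 5 says that for the comparison with TAU "comparable data will be directly collected through the OARS platform", and Section 3.1 likewise contrasts TAU baseline data with data gathered through OARS. Section 5 names the items to be fetched from the EHR because OARS does not transmit them: demographics, medications and billing. Kept visits and urine results are not among them. TAU data are EHR extracts submitted by clinic IT staff. Yet Section 5 also states: "All patient-level data will be collected via the EHR and transmitted to Q2i study staff via a secure file transfer system". Medical record identifiers are included "to link data across TAU and OARS conditions", and Section 3.1 describes the design as needing EHR abstraction only.

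On the population, Section 7.3 says that "the primary outcomes are meant to be evaluated with each clinic's entire patient population". Section 7.5, in explaining the language exclusion, makes participation depend on using OARS. Section 4.2 describes patients "who will contribute data to baseline and who will use the OARS platform when it is integrated into the EHRs".

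Section 3.2 measures retention, a primary outcome, by visits kept with the PCP and by length of stay. It gives no denominator, time zero or discontinuation rule. Section 6.3 compares an index visit, not defined, with 6 months after implementation.

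**The concern.** Take a patient on MAT on the go-live date who does not come back. If entry to OARS requires a visit after go-live, and OARS outcomes are read from the platform, this patient never becomes an OARS patient. The loss is charged to TAU or to neither condition. The carried-over patients who remain have all survived their first visit interval, whereas the EHR-based TAU data have no such entry step. Apparent retention under OARS can then exceed the truth with no effect of the software.

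Section 5 moves current TAU patients to OARS at each clinic, so the question arises at all six go-lives. Two analysts could each follow the text faithfully and obtain different results on a primary outcome.

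**Working it through.** **Plan's own figure.** There is none to reproduce: the documents give no retention rate, monthly loss or visit frequency. The rates below are assumptions.

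**Step 1: the non-returner under each reading.** Under platform entry and capture there is no visit, no enrolment and no OARS record, so the patient is absent from the OARS denominator. Under a full EHR roster the patient counts as OARS from go-live, with no further stay and no visits.

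**Step 2: which outcomes move.** Let f be the share of the go-live roster that never returns, with the clock starting at go-live.

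- Total visits kept: a non-returner adds 0 either way, so there is no change.
- Proportion of opioid-free urine tests: a non-returner gives no later test either way, so there is no change.
- Number of patients treated: leaving non-returners out can only lower the OARS count or leave it as it is.
- Mean length of stay, visits per patient, proportion retained: the total is unchanged while the denominator falls from N to N(1−f), so the result is multiplied by 1/(1−f).

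**Step 3: illustration for carried-over patients.** Assume monthly visits, constant monthly loss h and no OARS effect. Missing the first interval gives f = h. True 6-month retention on the full roster is (1−h)^6. Among those seen it is (1−h)^6/(1−h) = (1−h)^5.

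| h | Full roster (1−h)^6 | Seen only (1−h)^5 | Spurious gain, points | Factor 1/(1−h) |
|---|---|---|---|---|
| 3% | 83.3% | 85.9% | 2.6 | 1.03 |
| 5% | 73.5% | 77.4% | 3.9 | 1.05 |
| 8% | 60.6% | 65.9% | 5.3 | 1.09 |
| 10% | 53.1% | 59.0% | 5.9 | 1.11 |
| 15% | 37.7% | 44.4% | 6.7 | 1.18 |

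The last column also applies to mean stay after go-live. New patients, who have no go-live interval to survive, dilute these figures. Their share is not given.

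**Step 4: the opposite reading.** If Section 4.2 restricts baseline to patients who later use OARS, TAU patients are selected for still being there at go-live, and their retention to that date is close to 100% by construction. With exponential loss at an assumed monthly hazard of 3%, 6% or 10%, unselected retention at 4 months (the baseline length for clinics one and two in Section 5) would be 88.7%, 78.7% or 67.0%. TAU would then be overstated by up to 100 − 88.7 = 11.3, 100 − 78.7 = 21.3 or 100 − 67.0 = 33.0 points. This works against OARS and can exceed the gain in Step 3.

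**The case against.** The strongest reply is that the authors mean the whole roster. The word linking the two sentences in Section 5 makes the shift of all TAU patients a consequence of the entry rule, which suggests that seen means under care. The all-EHR statement, the linked identifiers and the population named in Section 7.3 all point the same way, and on them a patient never enrolled on the platform can still be found and counted. Section 5 also refers to a data collection tool and specifications that are not part of these documents and may contain an active-patient rule.

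These points stand as far as they go. A reader might infer that the plan definitely excludes non-returners; it does not say so. But the full-roster reading is not stated either, and it conflicts with platform capture of the comparison data.

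Two objections to the size also stand. A 6-month retained proportion is not a listed endpoint, so the table is an illustration. And if time starts at an index visit in both conditions, the free interval in the formula disappears, although losses between go-live and that visit must still be assigned to a condition.

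Two further inferences are tempting and unsupported. One is that the plan as a whole is biased towards OARS: the Section 4.2 reading pushes the other way. The other is that urine results improve through the same mechanism: a patient who never returns supplies no later test under either rule.

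**Conclusion.** The concern holds as a conflict in the plan with a conditional bias on a primary outcome. The roster at go-live, the retention denominator and time zero are undefined, and the data-source statements contradict one another.

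The upward bias in length of stay or per-patient retention rests on three conditions: entry needs a visit after go-live, OARS outcomes come only from the platform, and time runs from go-live. Its size depends wholly on the assumed loss rate, and it concerns carried-over patients alone. The sign of the overall TAU-to-OARS distortion cannot be determined from the documents.

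The matter should be settled before outcome data are seen, because choosing the denominator afterwards would itself invite bias.

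**What to change.** Reconcile Sections 3.1, 4.2, 5, 7.3 and 7.5, and write into Section 6.3:

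- One rule for an active MAT episode, applied to the EHR at fixed calendar dates in both TAU and OARS periods.
- Every patient active on the go-live date counts as OARS from that date, whether or not seen again or enrolled on the platform.
- Later use of OARS is not a condition for inclusion in TAU.
- Retention is taken from the EHR in both conditions, with the same time zero, and the index visit is defined.
- Carried-over and new patients are reported separately. Carried-over patients have already stayed through TAU and may drop out less even on a full roster, which the roster rule alone does not cure.
- Platform enrolment is kept only as an engagement measure for the secondary aim.

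The cost is one EHR query per clinic and period, plus wording. Section 4.2 already requires an established EHR, and Section 5 already plans the extracts and the linking identifiers. The OARS retention figure may come out less favourable.

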Despite the staggering overdose deaths and the increasing rates of OUD across the country, the number of providers who have waivers to prescribe or dispense buprenorphine under the Drug Addiction Treatment Act of 2000 (DATA-2000 waivers) cannot close the gap for the number of patients who need treatment.^{13,14} Moreover, among those who enter medication-assisted treatment (MAT) for OUD, the majority discontinue early in the course of treatment.^{15,16} Current gaps in the referral process contribute to delays to care, with the obvious solution being the improvement of systems to address these issues and to expand the use of MAT for the many patients out of care.¹⁷ Office-based buprenorphine treatment is a safe and effective form of MAT that can be delivered in most primary care settings,¹⁸ and retention in treatment is associated with decreased morbidity and mortality among people with OUD.^{19,20} Another factor that interferes with primary care providers treating patients in their practices using buprenorphine involves national clinical guidelines that recommend treatment be accompanied by psychosocial interventions,^{21,22} but such interventions are not available within many practice settings,^{23,24} and evidence for effective psychosocial interventions for buprenorphine treatment is limited.²⁵

There exists an outstanding opportunity for the power of the electronic health record (EHR) to be harnessed and leveraged to assist primary care providers (PCPs) in being able to have immediate reports on the response (or lack of) to MAT among their patients (e.g. monitoring attendance to clinic visits; reviewing urine drug screen results) and to track attendance by their patients with their counselors and affiliated psychosocial providers. Examples of successful application of software solutions within the electronic health record for management of chronic diseases other than addiction include products for screening and treating HCV,²⁶ lung cancer,²⁷ and diabetes.²⁸ These studies and projects provide a sound premise for the current proposal to develop and evaluate an electronic health record tool to improve outcomes when treating OUD in the setting of primary care clinics.

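### The plan contradicts itself on whether OARS-period outcomes come from the EHR or from OARS; unless OARS only relays EHR records, the outcome source changes with treatment

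*Combined protocol and SAP*

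**What the plan says.** All references are to the combined protocol and SAP.

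- **TAU months.** Section 5 makes clinic staff the suppliers of EHR data: "IT staff will be responsible for submitting requested data elements from the" clinic's EHR. "Baseline data will provide an assessment of TAU for up to a period of four" months in clinics one and two, eight in clinics three and four, and 12 in clinics five and six.
- **OARS months, read as OARS data.** Section 3.1 says "baseline data collected under TAU will be compared to corresponding data collected through OARS". Section 5 says "To compare outcomes under the OARS condition to those that occurred under TAU, comparable data will be directly collected through the OARS platform". It then limits what the EHR still has to supply: "Data elements of interest (patient demographics, medications, and billing information) that are not transmitted through OARS will be obtained from each" clinic's EHR.
- **OARS months, read as EHR data.** The sentence after the Section 3.1 comparison says "This study design necessitates data collection only through EHR data review and abstraction". The next paragraph of Section 5 says "All patient-level data will be collected via the EHR and transmitted to Q2i study staff via a secure file transfer system".

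The primary outcomes (Section 3.2) are the number of patients treated with MAT, retention (visits kept and length of stay), and the proportion of urine tests free of opioids. No section names a source for each outcome in each period. Section 5 points to a data collection tool that is not among the documents available for this review and may name the sources.

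**The concern.** All three primary outcomes are counts or proportions of recorded events, so they depend on how completely events are recorded. If visits and urine results come from EHR extracts under TAU and from the platform afterwards, any difference in completeness between the two sources becomes part of the TAU-versus-OARS contrast. A stepped-wedge design protects against calendar trends because clinics start at different times. It gives no protection here, because source and treatment would change together, in the same month, at every clinic. The plan includes no comparison of the two sources.

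**Working it through.** The plan gives no figure to reproduce on this point. The check has three parts.

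**1. Which outcomes are exposed.** The elements that Section 5 lists as coming from the EHR in OARS months are set against the primary outcomes.

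| Primary outcome | Possible EHR check in OARS months from the listed elements |
|---|---|
| Number treated with MAT | Yes, medications |
| Length of stay | Partly, medications and billing |
| Visits kept | Partly, billing |
| Opioid-free urine tests | None listed |

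Section 1.1 treats attendance and urine screens as EHR content ("monitoring attendance to clinic visits; reviewing urine drug screen results"). It also says that the software inside OARS draws on both the EHR and patients, and that attendance and urine results feed it. It does not name the origin of each item.

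**2. Whether the design can separate source from treatment.**

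- TAU clinic-months, at most: 2 × (4 + 8 + 12) = 48.
- OARS clinic-months: 6 × 6 = 36 if the six-month focus in Section 6.3 is read as the first six months, or 6 × 8 = 48 if all eight months in Section 5 are used.

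Section 6.3 does not specify a model. I assume clinic effects, month effects, an OARS indicator and a source indicator, for an outcome with no EHR counterpart in OARS months.

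| Data used | Six-month window | Eight-month window |
|---|---|---|
| EHR under TAU, OARS platform afterwards | 6 + 17 + 1 + 1 = 25 columns, rank 24 | 6 + 19 + 1 + 1 = 27 columns, rank 26 |
| EHR in both periods (no source term) | 24 columns, rank 24 | 26 columns, rank 26 |
| EHR series kept beside the OARS series | 25 columns, rank 25 | 27 columns, rank 27 |

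For the six-month window the first two rows use 48 + 36 = 84 clinic-months, and the third uses 48 + 2 × 36 = 120 records. The first row is one short of full rank because the source and OARS indicators are the same column; that follows from the definition and needs no computation. The useful result is in the other two rows: an EHR series in the OARS months makes the OARS effect estimable.

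**3. What a capture difference would do.** The documents give no capture rates. The rates below are assumptions, with no true effect of OARS.

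*Visits kept.* Apparent rate ratio = capture under OARS ÷ capture under TAU.

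- 0.95 / 0.90 = 1.056
- 0.90 / 0.95 = 0.947
- Equal capture: 1.00

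*Urine.* Let p be the true opioid-negative proportion, and let n and q be the capture of negative and positive tests in the OARS source. TAU capture is taken as unrelated to the result. Apparent proportion = pn / [pn + (1 − p)q].

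| p | n = 0.90, q = 0.95 | n = 0.95, q = 0.90 |
|---|---|---|
| 0.40 | 0.387 (−1.3 points) | 0.413 (+1.3) |
| 0.60 | 0.587 (−1.3) | 0.613 (+1.3) |
| 0.80 | 0.791 (−0.9) | 0.809 (+0.9) |

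If loss is unrelated to the result (n = q), the shift is zero. If instead all negatives are captured and only positives are lost, then for p from 0.50 to 0.80 the apparent proportion rises by 0.8 to 1.3 points at q = 0.95, 1.6 to 2.6 points at q = 0.90, and 3.3 to 5.6 points at q = 0.80.

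**The case against.** The strongest reply is that OARS is only a conduit for EHR records, so nothing changes at crossover. There is good support for this:

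- The Section 5 statement that all patient-level data come through the EHR is unqualified, and the sentence after it applies the transmissions to linking patients across both conditions.
- Section 4.2 describes the research as medical record review.
- Section 4.3 excludes clinics that cannot allow OARS to be integrated in the EHR, and Section 6.3 also assumes integration, so a standalone OARS is not what is planned.
- Section 5 speaks of elements transmitted through OARS, which suits a relay.
- Sections 3.1 and 5 each place the two statements close together, which suggests that the authors saw no conflict.

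The reply also notes that the short list of EHR elements need not be exhaustive, that Section 3.2 takes further service-delivery detail from EHR, claims and OARS for the exploratory outcomes, that the unseen data collection tool may settle the question, and that the capture rates above are invented.

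Much of this stands. The relay reading is plausible, the effect may be nil, and visits could be partly cross-checked. But integration does not establish which record lies behind each outcome, and no section says that visit and urine results held in OARS are the EHR records. Section 3.2 lists OARS beside the EHR and claims as a source, and Section 6.1 names data collected in the platform among the records to keep, although engagement data alone could explain the latter. Nothing cited settles the source of urine results. An analyst who follows the Section 5 sentence on comparison data would use platform data for the OARS months.

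**Conclusion.** The concern holds. Sections 3.1 and 5 each contain both statements about the OARS period, and nothing in the current text reconciles them. That contradiction is certain; the bias is conditional. It is nil if OARS relays EHR records or if the two sources are equally complete. Otherwise its size and direction are unknown. Under the assumed 90% and 95% capture rates it is about 5 to 6% on visits kept and about 1 point on the urine proportion, in either direction; if only positive tests were lost, it could reach 5.6 points at 80% capture. The exposure is clearest for urine results, for which no EHR element is listed in the OARS months. That visits and urine results change source is inferred from the short list of elements still drawn from the EHR, so confidence in an actual switch is medium. The matter should be settled before analysis, because the design cannot separate the two effects afterwards unless an EHR series exists for the OARS months.

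**What to change.** Reconcile Sections 3.1 and 5 so that each primary outcome has one named source in both periods.

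- **In Section 5**, replace the sentence on collecting comparison data through the platform with: *All primary outcomes will be taken from the clinic EHR under one extraction specification in both TAU and OARS months, for all eligible MAT patients.* This agrees with Section 7.3, which intends the primary outcomes to cover each clinic's whole patient population.
- **In Section 3.1**, describe the comparison data as coming from the EHR during the OARS period.
- **Keep platform data** for the engagement measures of the secondary aim and for the time stamps used in the return-on-investment work.
- **If OARS only relays EHR records**, it is enough to state this and list the EHR field behind each primary outcome.

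The cost is small. For a relay it is one statement and a field list. Otherwise, visit and urine-result fields are added to the OARS-period EHR transfers, if they are not already there. Those transfers already run and carry the medical record identifier, and the TAU specification can be reused.
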